1.3 Rationale for Intra wound Antibiotics and Gentamicin Use

Some promising alternatives to vancomycin are aminoglycoside antibiotics, including gentamicin. These antibiotics are on the order of 10-100 times cheaper than vancomycin, with pricing in Tanzania less than \$0.50 for one 80mg vial of liquid gentamicin compared with approximately 20 USD for 1g of vancomycin powder¹². Aminoglycosides cover a broad spectrum of gram-negative and gram-positive bacteria, including both *staphylococcus aureus* and *coagulase-negative staphylococcus*, the two most common bacteria in fracture-related infection (FRI)¹³. Aminoglycosides impregnated into polymethylmethacrylate (PMMA) beads have been shown to reduce infection in open fractures, but a second surgery is required to remove the beads¹⁴. PMMA also costs \$80-100 per 40-gram bag, which can be cost-prohibitive in low-resource settings.

A lower-cost alternative is injection of aqueous aminoglycosides after wound closure. Reduced rates of infection have been observed after local gentamicin injection in an animal model¹⁵ and

one large retrospective cohort study found a 50% reduction in the odds of deep and superficial infection after prophylactic local injection of aminoglycosides for open tibia fractures compared to no local antibiotics¹⁶. Although promising, the latter study's limitations are numerous, including retrospective, non-randomized design, absence of masking, and variability in treatment protocols and definitions of infection. There remains a clear gap in knowledge regarding the efficacy of locally-administered gentamicin in preventing fracture-related infection in open fractures.

The *GO-Tibia trial, A Masked, Randomized Controlled Trial to Evaluate Local Gentamicin versus Saline in Open Tibia Fractures*, will address these gaps in the literature.

2.0 STUDY AIMS AND HYPOTHESES

The study described herein is a single-center pilot trial to evaluate the feasibility of necessary protocols including, recruitment, retention, masking and concealment, intervention, and follow-up. The described pilot study will establish effect sizes for appropriate power calculations for a subsequent definitive trial.

The overarching objective of the definitive trial is to test whether injection of intraoperative local gentamicin impacts the rate of fracture-related infection following GA Type I, II or IIIA open tibia fractures in Tanzania. We hypothesize that the risk of fracture-related infection will be reduced by the intraoperative use of locally administered gentamicin at the time of wound closure.

2.1 Definitive Trial Specific Aims:

1. Compare the rate of fracture-related infection at one year after intraoperative local gentamicin injection or intraoperative local saline injection among adults treated operatively for GA Type I, II, or IIIA open tibia fractures. [Primary aim]
2. Compare the occurrence of 1) nonunion, and 2) unplanned fracture-related reoperation after intraoperative local gentamicin injection or intraoperative local saline injection among adults treated operatively for GA Type I, II, or IIIA open tibia fractures. [Secondary aims]
3. Evaluate the economic impact of fracture-related infection (FRI) after open tibia fractures in Sub-Saharan Africa including direct medical costs and lost productivity. [Secondary aims]

Null hypothesis: There is no difference in the rate of fracture-related infection between local gentamicin administration and saline administration for adult patients with GA Type I, II, or IIIA open tibia fractures treated in Sub-Saharan Africa.

Alternative hypothesis: Intraoperative local gentamicin administration decreases the occurrence of fracture-related infection in adult patients with GA Type I, II, or IIIA open tibia fractures treated in Sub-Saharan Africa.

2.2 Feasibility Trial Specific Aims:

Outcomes include rates of screening, enrollment, randomization, allocation, reliability of intervention, subject retention, and data completeness.

Specifically, feasibility outcomes are:

1. Recruitment: number of patients screened, number and proportion of patients screened that are eligible, enrolled, randomized, and receive intervention.
2. Retention: number and proportion of randomized patients who attend each follow-up visit. We aim for an adherence rate at follow-up of 80% at one year.
3. Data collection completeness: proportion of fracture-related infection criteria, EuroQol-5 Dimensions, 3-level questionnaire (EQ-5D), Function Index for Trauma (FIX-IT), and Modified Radiographic Union Score for Tibia (mRUST)¹⁷ indices complete at each time point.
4. Solution quality control: confirmation of the ongoing sensitivity of standard organisms to trial solutions via interval testing.
5. Masking and concealment: determination of the continued masking of surgeons to solution identity via intraoperative surgeon survey.
6. Evaluation of primary and secondary outcomes: reliability of fracture-related infection and mRUST scoring¹⁷, radiographic image quality, and completeness of EQ-5D and FIX-IT.

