Diagnosis and Main Inclusion Criteria	All patients 18 years of age or older who present to Muhimbili Orthopaedic Institute (MOI) for treatment of Gustilo-Anderson (GA) Type I, II or IIIA open tibia fractures will be screened for participation. Eligible patients must present to the hospital within 48 hours of their injury and receive surgical debridement of their open fracture wound within 7 days of their injury. The open wound must be primarily closable at the index debridement.
Treatment Groups	The pGO-Tibia trial will compare two solutions: 1) aqueous gentamicin solution (2mg/mL) in normal saline, or 2) normal saline only. A minimum of 5mL and a maximum of 40 mL of either solution will be injected into the fracture site immediately following primary closure of the traumatic wound.

Randomization	Allocation to the study groups will be performed using a web-based randomization. The randomization sequence was generated using randomly permuted blocks of 4, 6, and 8 with a 1:1 allocation ratio.
Study Outcomes	The definitive trial primary outcome is occurrence of FRI. Secondary outcomes of the definitive trial are the occurrence of 1) nonunion, and 2) unplanned fracture-related reoperation within 12 months of definitive fixation. Definitive trial subsidiary outcomes include health-related quality of life, radiographic healing, and clinical healing. A blinded adjudication process will judge each study event on occurrence of FRIs, nonunions, and unplanned fracture-related reoperations.
Feasibility Outcomes	This pilot trial will focus on the following feasibility endpoints: Recruitment: number of patients screened, number and proportion of patients screened that are eligible, enrolled, randomized, and receive intervention. Retention: number and proportion of randomized patients who attend each follow-up visit. Data collection completeness, solution quality control, masking and concealment, and evaluation of primary and secondary outcomes (reliability of fracture-related infection and mRUST scoring, radiographic image quality, and completeness of EQ-5D and FIX-IT).
Follow-Up	Study participants will be followed at 2 weeks, 6 weeks, 3 months, 6 months, 9 months, and 12 months from their fracture.
Sample Size	50 individuals per arm will be included in the feasibility trial.

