4.7.2 Definitive Trial Outcomes

Primary Outcome

The primary outcome is occurrence of *fracture-related infection* (FRI) a binary variable. FRI diagnosis is likely to peak between 3 and 6 months after surgery and has a non-normal time-to-event distribution, with incident cases rarely presenting later than 12 months after surgery. Any of the four following diagnostic criteria are confirmatory for infection: (1) fistula, sinus or wound breakdown; (2) purulent drainage from the wound or presence of pus during surgery; (3) phenotypically indistinguishable pathogens identified by culture from at least two separate deep tissue/implant specimens; or (4) presence of microorganisms in deep tissue taken during an operative intervention, as seen on histopathological examination.

Secondary Outcomes

The following secondary outcomes will be assessed:

1. Occurrence of nonunion, a binary variable, as defined by:
 - a. Any unplanned reoperation for promotion of bone healing; OR
 - b. mRUST ≤ 10 AND either: FIX-IT score ≤ 11 at 12 month follow-up, OR recommendation by treating surgeon for nonunion repair surgery.
2. Occurrence of unplanned fracture-related reoperation, a binary variable, for infection, wound healing, or fracture union, excluding removal of implants for prominence/irritation. This may include but is not limited to:
 - a. Irrigation and debridement of surgical incisions or open fracture wounds due to infections or wound healing problems;
 - b. Revision wound closure for dehiscence;
 - c. Soft tissue coverage procedure for infected or necrotic wound;
 - d. Fracture delayed union or nonunion surgery (such as bone grafting or implant exchange);

- e. Reoperation for hardware or prosthesis failure due to infection or bone-healing problems;
- f. Amputation for infection, wound or fracture healing problem.

Subsidiary Outcomes

The following subsidiary outcomes will be assessed:

1. Radiographic healing via the mRUST score, an ordinal scale ranging from 4 to 16.
2. Clinical healing via the FIX-IT score, an ordinal scale from 0-12 that encompasses two domains, ability to weight-bear and pain at fracture site, each scored from 0-6: ability to weight-bear and pain at fracture site.
3. Health-related quality of life via EQ-5D.
4. FRI suggestive criteria, including clinical (wound redness, fever) and radiographic signs (sequestrum), elevated serum inflammatory markers, and new onset or increased wound drainage.

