5.0 STATISTICAL PLAN

5.1 Preliminary Sample size determination:

This study seeks to explore if local antibiotics are effective in reducing infection. Existing literature estimates the rate of infection after intramedullary nailing for open-tibia fracture at 6-21%, with higher rates seen in developing countries^{23,24}. Based on the previous randomized controlled trial conducted at MOI, the rate of deep infection in patients with open tibia fractures who do not receive local antibiotics during operative management was estimated to be 12%. For a relative risk reduction of 50% in the rate of deep surgical site infections, with an alpha (two-sided) of 0.05 and power of 0.80, the estimated sample size was 712 patients (356 per group). Assuming a loss to follow-up of 20%, the final sample size needed was determined to be 890 patients. Given the anticipated enrollment of 15 participants per month, enrollment would take approximately 5 years for a single center study. The study described herein is a pilot trial with a 1-year enrollment period to include 100 patients, approximately 10-20% of the necessary sample size for the definitive trial.

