5.2 Statistical Methods

Feasibility outcomes described in 4.7.1 will be summarized using means and proportions, without the use of inferential statistics. Given the principle feasibility aim of this pilot trial, the following statistical methods are described primarily for planning purposes. Statistical methodology to be performed in the analysis of each primary, secondary, and subsidiary outcome is outlined below. The statistical analysis plan (SAP) will provide additional detail on statistical analysis and will be modified as necessary based on data collected in this pilot trial.

Outcomes Analysis Planned for Definitive Trial

Outcome	Data	Method of analysis
---------	------	--------------------

Primary		
Rate of fracture-related infection	FRI criteria	Relative Hazard as estimated by two-sided binomial regression with the complementary log-log link, with a type I error rate (alpha) of 0.05.
Secondary		
Rate of unplanned reoperation	Review of complications	Fisher's exact test on the 2×2 cross-tabulation
Rate of nonunion	Nonunion criteria	
Subsidiary		
Quality of Life	EQ-5D	
Inflammatory Markers	CRP	
Radiographic Healing	mRUST	
Clinical Healing	FIX-IT	
Direct costs	TM Analysis	
Indirect costs	WPAI	
FRI Suggestive Criteria	FRI criteria	Fisher's exact test on the 2×2 cross-tabulation

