5.2.1 Primary pre-specified analysis

Outcome Variable: the occurrence of FRI, as a binary outcome. We will denote this by Y_i , for person i . For each individual, we also record the time under observation, T_i . This value will be censored at the end of the follow-up time. [17]

Primary Analysis: the primary analysis will be conducted as a binomial regression with the complementary log-log link. This allows the available person-time to be used.

The estimated effect will be the relative hazard.

The analysis will be two-sided, with a type I error rate (alpha) of 0.05. Because there is no intention of including patients from this pilot trial into a subsequent definitive study, each trial (pilot and definitive) is completely separate, with an independent alpha.

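### Section 2.0 promises effect sizes for powering the definitive trial, but a pilot of 50 per arm, with about 9 expected infections, cannot supply the FRI treatment effect

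*Combined protocol and SAP*

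**What the plan says.** The opening paragraph of section 2.0 gives the pilot two purposes. One is to evaluate the feasibility of the trial procedures. The other is stated without qualification: "The described pilot study will establish effect sizes for appropriate power calculations for a subsequent definitive trial". The next paragraph gives the definitive trial's objective as the effect of gentamicin on the FRI rate.

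The Study Summary fixes the pilot's size: "50 individuals per arm will be included in the feasibility trial".

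Section 5.1, headed as preliminary, sizes the definitive trial on infection. It takes a 12% control rate from an earlier trial at the same site and an assumed effect: "For a relative risk reduction of 50% in the rate of deep surgical site infections". With two-sided alpha 0.05 and power 0.80 it arrives at 712 patients, or 890 after 20% loss. It also gives a wider range: "Existing literature estimates the rate of infection after intramedullary nailing for open-tibia fracture at 6-21"%.

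Elsewhere the pilot is confined to feasibility. The Study Summary, 2.2 and 4.7.1 list recruitment, retention, completeness, solution quality, masking and outcome reliability, and none of them lists an effect estimate. Section 5.2 summarises feasibility outcomes without inferential statistics and says the efficacy methods are set out mainly for planning. FRI and its analysis stand under "Definitive Trial Outcomes" (4.7.2) and "Outcomes Analysis Planned for Definitive Trial" (5.2). Section 5.2.1 nevertheless says that "each trial (pilot and definitive) is completely separate, with an independent alpha".

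**The concern.** An effect size for a power calculation has to be either chosen on clinical grounds or estimated with useful precision. Section 2.0 says that this pilot will establish it, but a binary outcome with a rate near 10% yields very few events in 100 patients. An estimate resting on so few events mostly reflects chance.

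The definitive trial would take 890 patients and about five years at one centre (5.1). If its size were reset from the pilot's observed effect, a lucky pilot would lead to an underpowered trial, and an unlucky one would suggest abandoning a treatment that works. The reader cannot rule this out: 2.0 promises effect sizes, 5.1 is labelled preliminary, and 5.2 allows the SAP to be modified in the light of pilot data.

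**Working it through.** **Inputs.** 50 per arm (Study Summary). Control rate 12%, range 6% to 21%, 50% relative reduction, two-sided alpha 0.05, power 0.80, 20% loss (all 5.1). Assumption: the deep-infection rate in 5.1 stands for FRI.

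**1. The plan's own figure.** With p1 = 0.12, p2 = 0.06 and mean 0.09, the pooled-variance formula is

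n = [1.96·√(2·0.09·0.91) + 0.842·√(0.12·0.88 + 0.06·0.94)]² / 0.06² = 355.9 per arm.

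That is 356 per arm, 712 in total, and 712/0.8 = 890. Section 5.1 reproduces exactly.

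**2. What 50 per arm gives.** Expected events are 50·p1 + 50·p2. The standard error of the log risk ratio (RR) is √(1/a − 1/50 + 1/b − 1/50), where a and b are the expected events in each arm.

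| Control rate | Expected FRIs | SE of log RR | RR and 95% CI |
|---|---|---|---|
| 6% | 4.5 | 0.980 | 0.50 (0.07 to 3.41) |
| 12% | 9 (6 v 3) | 0.678 | 0.50 (0.13 to 1.89) |
| 21% | 15.75 | 0.496 | 0.50 (0.19 to 1.32) |

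After the planned 20% loss (40 per arm), 12% v 6% gives 7.2 events and a CI of 0.11 to 2.21. On the planned complementary log-log scale with equal follow-up and 50 per arm, the relative hazard is ln(0.94)/ln(0.88) = 0.48, SE 0.707, 95% CI 0.12 to 1.94.

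**3. Size needed for a modest precision target.** For an RR interval running from half to double the estimate, n per arm = [(1/p1 − 1) + (1/p2 − 1)] / (ln 2/1.96)². This gives 384, 184 and 98 at control rates of 6%, 12% and 21%, against 50.

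**4. What one event does.** Suppose the saline arm has the expected 6/50 and the step 1 formula is applied, with N = 2n/0.8:
- 3 gentamicin events (RR 0.50): n = 355.9, N about 890.
- 2 events (p2 = 0.04): n = [1.96·√(2·0.08·0.92) + 0.842·√(0.1056 + 0.0384)]² / 0.08² = 179.3, N about 448.
- 4 events (p2 = 0.08): n = [1.96·√(2·0.10·0.90) + 0.842·√(0.1056 + 0.0736)]² / 0.04² = 881.8, N about 2,205.

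**5. All possible pilots.** Every pair of event counts is weighted by its binomial probability under a true 12% v 6% with 50 per arm, and converted to N by the same formula. No benefit means at least as many gentamicin FRIs as saline FRIs.

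| Implied definitive N | Only the RR taken from the pilot, control held at 12% | Both observed rates taken |
|---|---|---|
| No benefit seen | 19% | 19% |
| Below 445 | 28% | 32% |
| 445 to 1,780 (half to double of 890) | 37% | 29% |
| Above 1,780 | 16% | 20% |

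About 8 of the 19 points for no benefit are exact ties. The first column matches the case in which the pilot effect replaces the assumed reduction. The second adds error in the control rate. With both rates taken, control rates from 6% to 21% give 32% down to 9% with no benefit, and 25% up to 40% within half to double of the size the formula gives at that rate.

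**6. Cost of a low figure.** A trial of 445 leaves 445·0.8/2 = 178 evaluable per arm. If 12% v 6% is true, z = [0.06 − 1.96·√(0.1638/178)] / √(0.162/178) = 0.018, so power is about 51%.

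**The case against.** The strongest reply is that this is one introductory sentence which names no outcome, and that the operative sections treat the study as a feasibility pilot. The feasibility outcomes contain no effect estimate, 5.2 bars inferential statistics for them and offers the efficacy methods mainly for planning, and 7.5 (Dissemination Policy) says the principal paper will report the feasibility endpoints. Section 5.1 already powers the definitive trial on a stated 50% reduction.

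Much of this stands. Tying the sentence to FRI is an inference, though the natural one. The feasibility text makes 2.0 look like an over-claim and not a working plan. But none of that text limits the sentence, and 5.1 is preliminary and open to revision, so the documents do not say which effect will govern the final calculation.

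It can also be said that infection may be commoner than 12%. At the upper figure of 40% in section 1.1, 50 per arm would meet the half-to-double target (44 needed), with an RR CI of 0.26 to 0.96. The site's own planning value is 12%, however, and no rate in the 6% to 21% range in 5.1 meets the target.

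Stronger readings are tempting but not supported:
- A reader might infer that the sponsor will put the pilot's observed effect into the power formula. No rule says so.
- A reader might infer from the independent alpha in 5.2.1 that a confirmatory FRI test is planned in the pilot. The headings in 4.7.2 and 5.2 and the planning caveat point the other way; the wording is merely loose.
- A reader might infer that the pilot is too small. It is too small for this one purpose only.
- Section 5.1 gives no source for its 50%, and the nearest figure in 1.3 concerns odds and a broader outcome ("one large retrospective cohort study found a 50% reduction in the odds of deep and superficial infection"). That is a separate question from whether the pilot can estimate the effect.

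**Conclusion.** The point holds as a mismatch between a stated purpose and the design. Section 2.0 promises effect sizes for powering the definitive trial. For FRI, 50 per arm gives about 9 events and an RR interval from an 87% reduction to an 89% increase. No control rate in the 6% to 21% range brings the upper limit below 1.

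The consequence is conditional. It arises only if the pilot's effect replaces the assumed 50% reduction. In that case 19% of pilots would show no benefit and 37% would give a usable size, taken as within half to double of 890.

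The result assumes that the 12% deep-infection rate applies to FRI, that the true effect is a halving, and that follow-up is complete. The planned 20% loss makes precision worse. The arithmetic in 5.1 and the size of the pilot as a feasibility study are not in question.

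**What to change.** In 2.0, replace the sentence with a statement that the pilot will inform recruitment, retention, data completeness and the overall FRI rate with its 95% CI. For scale, 9/100 has a Wilson interval of 4.8% to 16.2%. Add that the definitive trial will be powered on a pre-specified effect, as 5.1 already does, and not on the pilot's observed effect. In 5.2.1, state that any FRI comparison in the pilot is descriptive and reported with a confidence interval.

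The cost is a few sentences. Enrolment, data collection and endpoints do not change, and the combined analysis of both trials in 5.2.2 can still use the pilot data. The only loss is the claim that the pilot supplies an effect size.

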3.0 TRIAL DESIGN

3.1 Summary:

In the accompanying Clinical Research Protocol and Standard Operating Procedures document, we describe the protocols and procedures for a feasibility pilot trial for implementing a single-center, double-masked, individually randomized, placebo-controlled study on the efficacy of intraoperative local gentamicin for the prevention of fracture-related infection in open Gustilo-Anderson Type I-IIIA tibial fractures. The Clinical Research Protocol and Standard Operating Procedures document includes general trial information, aims and objectives, study design, trial procedures (including recruitment, enrollment, consent, randomization, masking, intervention, and follow-up protocols), and data management.

4.0 METHODS

4.1 Study Setting:

The GO Tibia randomized controlled trial will be conducted at the Muhimbili Orthopaedic Institute (MOI) in Dar es Salaam, Tanzania. MOI is a tertiary referral hospital with large catchment area and high volume of adult musculoskeletal trauma that, combined with its strong leadership and prior trial experience, has the capacity to manage this large-scale RCT.

4.2 Eligibility Criteria:

All patients presenting to the MOI emergency department age 18 years and older with an open tibia fracture will be screened for eligibility (Table 1). After surgical debridement, the surgeon will assess the wound to see if the wound can be primarily closed. If the wound can be primarily closed, the patient will continue with the RCT Study. If the wound cannot be primarily closed, the patient will be excluded from the study.

Table 1: Inclusion and Exclusion Criteria

Inclusion Criteria	Exclusion Criteria

1. Skeletally mature patients (>18 years old)2. Open tibial shaft fracture meeting the following criteria:
a. OTA Type 42b. Primarily closable woundc. GA I, II, or IIIA	
1. Time from injury to presentation > 48 hours2. Time from injury to surgery > 7 days3. Aminoglycoside allergy4. GA IIIB or IIIC open fractures5. Bilateral open tibial fractures6. Severe brain (GCS<12) or spinal cord injury7. Severe vascular injury8. Severe burns (>10% TBSA or >5% TBSA with full thickness or circumferential injury)9. Pathologic fracture10. History of active limb infection, ipsilaterally11. Unlikely to complete follow-up

Abbreviations: Orthopaedic Trauma Association (OTA); Gustilo-Anderson (GA); Glasgow Coma Scale (GCS); Total body surface area (TBSA)

4.3 Recruitment Strategy and Patient Screening:

Recruiting patients: All adult (over age 18) patients admitted to MOI for acute open tibia fracture will be considered for inclusion in this study. Patients will be evaluated by the on-call orthopaedic surgery resident. The study protocol will be introduced to the patient either by the

resident or research coordinator. Patients interested in enrolling will be consented. All consenting patients will be treated per institutional protocol with immediate systemic ceftriaxone administration for open fracture prophylaxis and urgent debridement and bony stabilization with either internal or external fixation at the discretion of the operating surgeon. The study protocol will not influence the surgical plan for management of study participants. Type of fixation will not affect participant inclusion or study protocol.

The surgeon will make a final assessment of the wound and exclude patients with a wound that is not amenable to primary closure. If the wound is determined amenable to primary closure, participants will be randomized intraoperatively by research coordinators after closure is complete to receive intra-operative local injection of either aqueous gentamicin solution (intervention) or normal saline solution (control).

